The assessment period described above will be completed prior to initiating treatment, and then after completion of treatment sessions #2, 4 and 6 and 8 (i.e. post-treatment), and 3 and 6 months following the end of treatment for a total of seven times. These assessment periods that occur following the start of treatment will also include questions about group climate, therapeutic alliance with the group clinician, treatment satisfaction, feedback about the treatment modality, and overall improvement since the participant began the pain program. The open-ended questions regarding treatment satisfaction and feedback on treatment modality will be collected by an unblinded staff member. Group Comfort Questions will be administered by an unblinded staff member at any time after session 8 (final group session). This assessment is optional. The window is from post-treatment until the participant is disenrolled.

Staff will send via USPS mail a reminder letter prior to the 3- and 6-month assessment periods.

As mentioned above, during the consent process research staff will provide participants with a response key to help answer questions asked during the telephone assessment periods. Participants may request research staff send another response key to them if they lose the key during study participation. Research staff will send the response key along with a cover letter via USPS mail.

Participants will be compensated \$25 for the completion of each assessment period via a check written from the Seattle Institute for Biomedical and Clinical Research (SIBCR). The check will be sent via USPS mail and accompanied by a payment cover letter.

The pre-treatment assessment period may take place up to four weeks prior to the start of the treatment groups for that particular cohort.

D6I. Randomization

Enrolled participants who complete the required baseline components (cognitive assessment, hypnotic and relaxation exercise, baseline data form, and pre-treatment assessment period) will be randomized in stratified blocks to ensure that participants with each sex/gender and pain type (neuropathic, non-neuropathic, mixed or undetermined) have an equal chance of being randomized to one of the 3 conditions. Stratification will assure that the treatment groups are balanced regarding each stratification variable, so that the estimated effect of the treatment is not biased due to differences in distribution of sex/gender or type of pain.

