Assignment to one of the 3 groups will be accomplished with a Microsoft Excel spreadsheet with random numbers created by the research manager with the guidance of the biostatistician. Only a research staff member who does not have access to study data during subject enrollment will conduct the randomization procedures. This randomization assignment will be entered into a password-protected database located on a VA secure drive. Research staff will complete a randomization case report form for each randomized subject that will be filed with study data.

The staff randomizing subjects will convey assignment to [name] via email with only a code number used i.e. no identifying information to identify the participant. [name] will then update the master list of participants, both research and non-research, of the clinic portion of the program.

Subjects will be sent a letter that outlines the schedule of treatment sessions they will attend.

Research staff will re-screen participants on approved mutable eligibility criteria (e.g. pain intensity, frequency, etc.) if 6 months or more has elapsed between the consent process and randomization.

Randomization may take place up to four weeks prior to the start of the treatment groups for that particular cohort.

D6m. Treatment Scheduling: Research and Non-Research Participants

Cohorts of study treatment groups will be offered beginning every four months. In each 4-month period, there will be two class options for each condition, one based in Seattle and one at American Lake. Thus, there will be six classes offered per four month period, or a total of 18 classes per year.

Trained instructors will commit to offering three groups per year: one of each treatment type. This will reduce the potential for therapist bias in on the outcomes. Up to 15 participants can be enrolled in each group treatment class.

[name] will maintain lists of group assignments (for both research and non-research participants) and coordinate the scheduling of group class appointments. Both [name] and the unblinded research staff member responsible for randomization will have access to this information and be available to provide back-up if [name] is absent or preoccupied.

As aforementioned, the research staff conducting randomization procedures will alert [name] that a research participant has been randomized.

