not testable, but we can look at the variables that were observed in groups with and without missing outcomes data. No association between observed variables and the group (missing vs. no missing) will be considered an indication that the data are missing at random. In addition, we will look at the reported reasons for missing values when available. If we can assume data are missing at random, we will use multiple imputation procedures. If there appear to be non-random missing outcomes data, we will use two methods designed to account for this: Heckman's selection models and pattern-mixture models, both of which model the joint distribution of the outcome and the missing mechanism. In the case of non-ignorable missing data, we will use both methods as a sensitivity analysis. If less than 5% of the data is missing and we can assume ignorable missing data, the following analysis will be performed.

Hypothesis 1 states that Veterans randomly assigned to receive eight group sessions of HYP or MM will report significantly greater pre- to post-treatment decreases in average pain than Veterans receiving eight sessions of ED. The response variable will be change in average pain intensity score from pre- to post-treatment (Pre-treatment score – Post-treatment score). This response variable will be analyzed using an analysis of covariance (ANCOVA) with treatment condition (HYP, MM, ED) as the explanatory variable and the baseline pain as a covariate.

Support for Hypothesis 1 would emerge if a significant treatment main effect is present after adjusting for the baseline covariate, and subsequent post-hoc analyses indicate larger baseline to post-treatment decreases in pain intensity in the HYP and MM conditions, relative to the ED condition. The overall significance level for the test of the null hypothesis that all three treatments have equal effect will be set to 0.05.

Although we anticipate that HYP and MM will have similar effects on the primary outcome variable, these analyses will also allow us to compare the relative effects of HYP and MM with each other, as part of the exploratory aims/analyses.

Pairwise comparisons of the treatment groups will be performed using Tukey method (see for example, Analysis of Messy Data Volume 1: Designed Experiments, Second Edition, by GA Milliken and DE Johnson. 2009, chapter 3).

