Addressing Aim 2 by testing Hypothesis 2. Hypothesis 2 states that baseline EEG activity will predict differential response to HYP and MM, such that those participants who have higher baseline levels of global theta, and lower baseline levels of left frontal gamma will respond to HYP, while participants with lower baseline levels of global alpha will respond to MM. We will test for this moderator using a linear regression analysis, with pre- to post-treatment change in pain intensity as the response (criterion) variable. Treatment Condition, absolute power of baseline theta, alpha, and (left frontal) gamma, and terms representing the interaction between treatment condition and each EEG bandwidth will be the explanatory variables. Significant Treatment Condition X Theta, Alpha, and Gamma interactions, with higher coefficients for baseline theta and lower coefficients for baseline gamma in the HYP group, and lower coefficient for baseline alpha in the MM group would support Hypothesis 2.

Additional exploratory analyses. In addition to testing the two study hypotheses, we propose a series of exploratory analyses (explained below) to take full advantage of the data collected to better understand the effects and potential mechanisms of HYP and MM. However, because these analyses are exploratory, we will report them as such. Any statistically

significant findings will be viewed as providing support for further, more definitive, testing in the future.

Effects of HYP and MM on secondary outcomes. To examine the potential effects of HYP and MM, relative to ED, on co-morbid conditions, we will repeat the ANCOVA analyses planned to test Hypothesis 1 for the secondary outcome variables (assessing pre- to post-treatment decreases in depression, anxiety, sleep disturbance, pain interference, PTSD symptoms) as the response variables, controlling for the respective baseline measures of these secondary outcomes. The response variable will be change in each outcome measure score from pre- to post-treatment (Pre-treatment score – Post-treatment score). This response variable will be analyzed using an analysis of covariance (ANCOVA) with treatment condition (HYP, MM, ED) as the explanatory variable and the corresponding baseline value for each secondary outcome measure as a covariate.

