Perceived global improvement is a secondary outcome measure but unlike the other secondary outcome measures it was not measured at baseline, hence a slightly different approach will be used for this secondary outcome measure. Instead of a change score, we will simply use ANOVA to compare perceived global improvement with treatment condition as the independent variable.

To assess the effect of each treatment on post-treatment ratings of global satisfaction (which has only 5 categories), we will use an ordinal polytomous logistic regression. Because we anticipate that *both* HYP and MM will have significant beneficial effects on outcomes, we do not anticipate large differences between these two interventions in the outcome measures. However, we think that it would be important to estimate differences in outcome between the two active treatments for descriptive purposes. To do so, we will perform pairwise post-hoc tests to compare the means of the three groups.

We will report both the p-value and effect sizes for the tests between the two conditions (HYP and MM) on outcomes. While the study was not powered to simultaneously test for the primary and secondary outcomes, it is reasonable to assume that the sample size of 80 participants per condition (determined to adequately power the primary hypotheses) will allow for reliable estimates of the effect sizes for secondary outcomes as well.

Longer-term effects of HYP and MM, relative to ED.

As part of our exploratory aims, we plan to assess the extent to which change in pain intensity, the primary outcome, is maintained at 3 and 6 months post-treatment, and to see if longer term changes in pain intensity differ between HYP and MM compared to ED. To assess this, we propose to use a Generalized Estimating Equations (GEE) approach, which accounts for the correlated nature of the data due to multiple observations of the same person over time. Response variables over time will be the change from pre-treatment to post-treatment, and pre-treatment to 3- and 6- months follow-ups, with intervention group and follow-up time as the main factors of interest (including a Group X Time interaction), and the pre-treatment value as the covariate. For the correlation matrix, we will assume an unstructured format, since there was no a priori reason to use a more structured matrix format. We will repeat these analyses for the secondary outcome measures mentioned above.

Mediation analyses.

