Power to test the primary study hypothesis. The primary study outcome variable is change in average pain intensity, as represented by the difference between the baseline and post-treatment average pain intensity measures. We have used this measure successfully in numerous previous trials.^{41, 42, 52, 105, 106} Anticipated effects for HYP are based on the changes observed in our previous HYP trials using the 0-10 NRS measure, plus our pilot study of HYP for low back pain treatment, reported in the

'Preliminary findings' section.

Anticipated effect sizes for MM are based on published studies of the effects of treatments that involve mindfulness that used 0-10 NRS measures.

Assuming a decrease in pain score of 0.3 points for the education group, 0.8, 1 and 1.4 for the HYP, and 0.6, 0.8 and 1 for MM, we calculated the sample size to find differences between pre-post treatment difference scores, with an alpha of 0.05, power of 0.80, and varying the standard deviation (SD) from 0.15 to 1 (to cover values observed) when using an ANOVA. Sample sizes of 80 completers per condition (total = 240) will have at least 80% power, even at the largest standard deviation.

Power for secondary and exploratory analyses.

The sample size calculations above take into consideration only the primary hypothesis of interest (that different treatment have different effects in changing pain intensity), which is the most important result this study can provide for the person affected with chronic pain. However, the sample size of this study is relatively large and will provide extremely useful and important information regarding secondary outcomes, mediators and moderators associated with pain intensity and EEG. The results will form the basis for continuing research not only to find treatments that are efficacious, but also to hypothesize mechanisms of action, which will be crucial in designing future studies.

Power Calculations (Sub-Study)

We focus our power calculations on the most innovative aspect of the supplemental study, that is, the objective measurement of sleep by means of wrist actigraphy in the context of non-pharmacological pain treatments.

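### The primary ANCOVA, the repeated secondary ANCOVAs and the power calculation treat participants as independent although every treatment class belongs to one arm; the 5% test is anti-conservative if class-specific correlation outweighs shared effects

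*Combined protocol and SAP*

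**What the plan says.** Section D6m (Treatment Scheduling) sets up one class per arm at each of two sites in every four-month period: "Thus, there will be six classes offered per four month period, or a total of 18 classes per year". It adds that "Trained instructors will commit to offering three groups per year: one of each treatment type". So class is nested in arm, while site, cohort and, in part, leader are crossed with arm.

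Section D6x (Statistical Analyses) tests Hypothesis 1 on pre-to-post change in pain with an "analysis of covariance (ANCOVA) with treatment condition (HYP, MM, ED) as the explanatory variable and the baseline pain as a covariate". The omnibus level is 0.05, and "Pairwise comparisons of the treatment groups will be performed using Tukey method". This plain model is stated for the case of under 5% ignorable missing data; otherwise multiple imputation applies, or selection and pattern-mixture models if data are not missing at random. For the exploratory secondary outcomes, "we will repeat the ANCOVA analyses planned to test Hypothesis 1 for the secondary outcome variables". The one correlation modelled in the main-study analyses is in the longer-term GEE, which "accounts for the correlated nature of the data due to multiple observations of the same person over time".

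Section D6z (Power Analyses) uses an ANOVA and concludes: "Sample sizes of 80 completers per condition (total = 240) will have at least 80% power, even at the largest standard deviation".

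**The concern.** People taught in the same class share sessions, leaders and each other's company, so their outcomes may be correlated. Because a class sits wholly inside one arm, variation specific to that class adds to the variance of the arm means and does not cancel in arm contrasts. A model with only arm and baseline pain does not see it. Site, cohort and leader effects act differently: they fall on all arms to a similar degree, largely cancel in the contrasts, and stay in the residual variance, which makes the unadjusted test conservative.

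At stake are the level of the primary omnibus test and its Tukey follow-up, the interval widths for the primary and secondary contrasts, and whether the stated 80% power holds in the least favourable scenario.

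**Working it through.** **Inputs from the documents.** 80 completers per arm; mean decreases of 0.3 (ED), 0.8 / 1 / 1.4 (HYP) and 0.6 / 0.8 / 1 (MM); largest SD 1; alpha 0.05 (D6z). Six classes per four-month period (D6m). The number of periods can be read in two ways:
- groups stop after cohort 12 (D6c): 12 × 6 = 72 classes, 240/72 = 3.33 completers per class;
- 36 months of enrolment (D2): 9 × 6 = 54 classes, 240/54 = 4.44 per class.

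**Assumed.** ICC of 0.01, 0.05 or 0.10, and the split between class-specific and shared correlation. The documents give neither.

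**1. The plan's own figure.** For 0.3 / 0.8 / 0.6 and SD 1, the overall mean is 0.567 and the squared deviations sum to 0.1267. The noncentrality is λ = 80 × 0.1267 = 10.13. With 2 and 237 df, power is 81.6%. The plan's claim reproduces under independence; 80% needs 78 per arm, so there is almost no slack. The other eight scenarios give 91% or more.

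**2. Power with a design effect.** DEFF = 1 + (m − 1) × ICC, and λ becomes 10.13/DEFF. This takes all correlation as class-specific and keeps 237 df.

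| Classes | ICC | DEFF | Weakest-case power |
|---|---|---|---|
| 72 | 0.01 | 1.023 | 80.6% |
| 72 | 0.05 | 1.117 | 76.9% |
| 72 | 0.10 | 1.233 | 72.4% |
| 54 | 0.01 | 1.034 | 80.2% |
| 54 | 0.05 | 1.172 | 74.7% |
| 54 | 0.10 | 1.344 | 68.4% |

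With class-level df (72 − 3 = 69), the 72-class values are 79.3 / 75.5 / 71.0%. At 237 df the other eight scenarios stay at 84% or more with 72 classes, and at about 81% or more with 54.

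**3. Type I error of the planned ANCOVA.** As an approximation, it is P(F > Fcrit/DEFF) with Fcrit = 3.03: 5.4 / 6.8 / 8.8% for 72 classes and 5.5 / 7.7 / 10.7% for 54. Simulation of the planned model (20,000 trials per setting, 24 classes per arm; ranges run over equal and random class sizes) gives, for ICC 0.01 / 0.05 / 0.10:
- all class-specific: 5.2–5.6 / 6.9–7.5 / 8.8–10.7%;
- half shared across arms: 4.9–5.4 / 5.3–6.2 / 6.1–7.4%;
- all shared: 4.7–5.0 / 4.4–5.0 / 3.5–5.0%.

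With equal class sizes, the direction turns at about (m − 1) × class-specific ICC = shared ICC. At m = 3.33 the shared part must be about 2.33 times the class-specific part to offset it.

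**4. The full decision rule.** Under the global null with all correlation class-specific, omnibus plus Tukey gives a false claim for at least one active arm in 1.7 / 2.2–2.5 / 3.0–3.7% of trials, against about 1.6% under independence. For both arms it rises from about 0.1% to at most 0.4%.

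**5. Offsets to the power loss.** Baseline adjustment multiplies the residual variance by (1 + r)/2, where r is an assumed pre-post correlation, SD 1 is the SD of change, and pre and post variances are equal. For r = 0.5 / 0.8 and 72 classes, weakest-case power is 91.5 / 85.7% at zero ICC, 88.2 / 81.4% at 0.05 and 84.6 / 77.1% at 0.10. Separately, if the 13% attrition cited in the précis applied to all 355 enrolled, 355 × 0.87 = 309, or 103 per arm (309/72 = 4.3 per class). ANOVA power is then 89.6 / 85.6 / 80.4% at ICC 0.01 / 0.05 / 0.10.

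**The case against.** The strongest reply is that the direction is unknown. Crossed leaders, treatment manuals, scripts read aloud (D6n) and fidelity review with feedback (D6u) all limit class-specific variation, and at ICC 0.01 the inflation is negligible. This stands. It is why the point is conditional, and a reader who infers that the test is inflated goes further than the documents allow. Yet none of these features removes class-specific variation. Site and cohort are also not among the named stratification factors (D6l), so shared effects balance across arms only approximately.

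A reader might also infer that the plan itself expects classes to differ, because the assessments "will also include questions about group climate, therapeutic alliance with the group clinician". That does not follow: these are questionnaire items, and Table 4 lists alliance as a mediator. Nor should the cap of 15 per class serve as the cluster size. Non-research attendees also fill those places, and 240 completers over 54 to 72 classes is 3.3 to 4.4 each.

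D6n does record session time so that differences can be controlled. That is a possible class-level covariate, but it is not in the stated ANCOVA and does not model correlation within classes.

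Equal ICCs in all arms may overstate the effect, since ED is designed not to reduce pain. With class variance in HYP and MM only, simulated type I error is 5.4 / 6.7 / 8.7%, against 5.7 / 7.7 / 10.2% with it in all three (random class sizes). That reduces the inflation without removing it.

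Finally, the secondary ANCOVAs are exploratory and carry no error-rate claim, the full decision rule is little affected, and baseline adjustment may restore the power. All of this is correct and limits the seriousness.

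**Conclusion.** The point holds in conditional form. The primary ANCOVA, its exploratory repeats and the power calculation assume independence that the class structure does not guarantee, and nothing in the plan would reveal whether the assumption fails.

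The likely size is modest. At an ICC up to 0.05, the omnibus type I error reaches about 7–8% if all correlation is class-specific, and is at or below 5% if all is shared. The stated 80% power is at risk only in the weakest scenario, and there mainly without credit for baseline adjustment or extra completers. All of this rests on the assumed ICC range, the unknown shared fraction, and a class count between 54 and 72. It should be fixed because the remedy is standard and cheap. It does not show that the primary result would be wrong.

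**What to change.** Before unblinding, specify for the primary ANCOVA and its Tukey comparisons (and, for consistency, the exploratory secondary ANCOVAs):
- a random intercept for class, defined as arm × site × cohort;
- site and cohort as fixed effects;
- a named small-sample degrees-of-freedom method, for example Kenward–Roger;
- participants who never attended a class treated as singletons;
- class carried into the imputation model whenever multiple imputation is used. That is likely, since D5 plans for 30% dropout and cites 12% in earlier studies.

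Report the ICC, and restate the D6z power over a stated range of ICC and class count. Keep a coded class identifier in the analysis file. Treatment data are already entered under the study code (D6n), so this does not depend on retaining the crosswalk.

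Cost: SAP wording, one identifier and wider intervals. If the true ICC is zero, weakest-case power falls by about 5 to 7 points: 81.6% to 75.0% without baseline credit, or 91.5% to 86.4% and 85.7% to 80.1% at pre-post correlations of 0.5 and 0.8. This was simulated for 72 classes with 72 − 15 = 57 denominator df, not with Kenward–Roger. In the same simulations, at ICC 0.01 / 0.05 / 0.10, the model held type I error at 4.0 / 4.5 / 4.9% with all correlation class-specific and 3.9 / 4.1 / 4.0% with half shared. It was conservative, at 3.6 / 3.2 / 2.7%, with all correlation shared. With an assumed 10% never-attenders as singletons it was 5.1 / 4.8% at ICC 0.05 / 0.10.

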Enrolled participants who complete the required baseline components (cognitive assessment, hypnotic and relaxation exercise, baseline data and demographic form, and pre-treatment assessment period) will be randomized in stratified blocks to ensure that participants with each sex/gender and pain type (neuropathic, non-neuropathic, mixed or undetermined) have an equal chance of being randomized to one of the 3 conditions. Stratifying in this manner will ensure the groups are balanced to reduce variation in outcome that is associated with each stratification variable.

Sub-Study:

Recruitment will follow the protocol of the main study. We propose to recruit up to ~~135~~ 180* 195** of the ~~343~~ 355** parent grant participants in order to ensure complete data from 117 participants, assuming a 15% drop-out rate. Based on our experience, we anticipate that at least 75% of the parent sample will elect to join the sleep study.

*Due to a higher attrition rate than anticipated, we have increased the enrollment number from 135 to 180 to ensure the 117 completers needed. A 13% attrition rate was determined based on the main study. The actual attrition rate for the sleep study is 27%.

** Enrollment number increased to allow for the recruitment of a full cohort in the final cohort of the study.

A. SPECIFIC AIMS

A1. Problem Statement

Main Study:

As many as 50% of male and 75% of female Veterans presenting to Primary Care report chronic pain¹⁻⁴, and reporting rates are even higher in specialty clinics.⁵⁻⁷ Among Veterans returning from Iraq and Afghanistan, 82% report chronic pain,⁸ and the prevalence of painful musculoskeletal, joint, and back problems tends to increase in the years following deployment.⁹ Prevalent co-morbidities among Veterans, such as substance use disorders, sleep dysregulation, mood disorders, and Post Traumatic Stress Disorder (PTSD) can amplify the experience of pain and complicate treatment.¹⁰⁻¹² In Veterans, the presence of co-morbid pain and anxiety is associated with increased service utilization,¹³ while co-morbid pain and substance use increases the risk of medication misuse.¹⁴ Pain is also associated with greater depression and anxiety,¹⁵ sleep dysregulation^{12, 16}, decreased quality of life,¹⁷ and lower self-reported health.¹⁸

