Post-Treatment Telephone Assessment Period	Up to 4 telephone assessments conducted within a one-week period	Once following end of treatment	About 45-60 minutes total	\$25
Post-Treatment Brain Activity Assessment	One in-person assessment at the UW Integrated Brain Imaging Center (IBIC) at the UW	Once following end of treatment	About 45-60 minutes	\$100

Post-Treatment Sleep Sub-Study Procedures	Wear actigraph on wrist, complete sleep/wake diary twice a day, call in wake/bedtimes twice in a day during a one-week period	Once following end of treatment	2 hours for sleep/wake diary, continuous for actigraph device	\$40
3 Month Telephone Assessments	Up to 4 telephone assessments conducted within a one-week period	Three months following end of treatment	About 45-60 minutes total	\$25
3 Month Sleep Sub-Study Procedures	Wear actigraph on wrist, complete sleep/wake diary twice a day, call in wake/bedtimes twice in a day during a one-week period	Three months following end of treatment	2 hours for sleep/wake diary, continuous for actigraph device	\$40, plus \$15-30 bonus as applicable
6 Month Telephone Assessments	Up to 4 telephone assessments conducted within a one-week period	Six months following end of treatment	About 45-60 minutes total	\$25
Bonus Payment: All telephone assessments completed	All seven telephone assessment periods are completed	Over 9-month period (see timeline listed above)	Totaling about 5-7 hours total over a 9-month period	\$50
Open Label Phase Study (cohorts 1-9)	Two telephone assessments, 8 treatment sessions	Following completion of the main phase of the study	About 13 hours over a 3-month period (assessments and treatment sessions included)	\$10 per assessment completed

D6t. Study Data

Main Study:

The following is a list and description of the data measures included in the study. We list the demographic and descriptive information we propose to collect from the study participants in the next paragraph. The primary outcome, secondary outcome, covariates (variables to control for in planned analyses if needed), and mechanism (mediator and moderator) variables for this study are listed in Table 4 (page 33). Details regarding a subset of the key measures are provided below. All outcome measures will be administered by research staff members blind to group allocation.

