We will then apply an autoregressive cross-lagged model to investigate the cross-lagged relationship between actigraphically measured sleep duration and pain outcomes from the parent project. For each of the two intervention groups, we will use an autoregressive regression model on sleep duration with subjective pain as the covariate of interest, and our objective will be to test the regression coefficient for this covariate against zero (two-tailed). We will account for the variance in sleep duration at the post-intervention and follow-up time points that is explained by sleep duration at the respective immediately preceding time point, ρ^2 , where the estimated value for ρ is drawn from our previous data set described above ($\rho=0.122$). With 39 subjects, we will have 80% statistical power, at a type I error threshold of $\alpha=0.05$, to detect a cross-lagged relationship between sleep duration and subjective pain at the immediately preceding time point if this relationship explains at least 17.3% of the variance (nQuery 7.0, Elashoff, 2007).

HUMAN PARTICIPANTS SECTION

1. Risk to Participants

1a. Human Participants Involvement and Characteristics

We plan to enroll up to ~~343~~ 355 participants into the study. Male and female participants 18 years of age or older who have chronic pain will be approached to participate in the study. Participants will be recruited from clinics at the Seattle and American Lake Campuses of VAPSHCS, as well as community-based outpatient clinics (CBOC).

Veterans will be recruited from several clinics and service lines at VAPSHCS: the Rehabilitation Care Service (which includes the Polytrauma Network Site for the northwest four

states, the Multiple Sclerosis Clinic/Center of Excellence, Prosthetic/Limb Loss Clinic, and Musculoskeletal Clinic), and the Spinal Cord Injury Service. Each of these clinics sees 200-500 new Veteran patients per year and carries an ongoing patient load of 200 – 400 patients. We will also recruit patients from Primary Care as needed, which carries an ongoing patient load of 19,000 patients per year.

Participants will also be recruited from VA community-based outpatient clinics (CBOC).

1b. Sources of Materials

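### The trial randomises within strata of sex/gender and pain type, but the primary ANCOVA, the secondary ANCOVAs and the GEE omit both factors, so the reported standard errors and tests are mildly conservative.

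*Combined protocol and SAP*

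**What the plan says.** **Randomisation.** The Précis (Sample Size and Population) and D6l say that participants who complete baseline "will be randomized in stratified blocks to ensure that participants with each sex/gender and pain type" have an equal chance of each condition. Two reasons are given. The Précis gives a variance reason: "Stratifying in this manner will ensure the groups are balanced to reduce variation in outcome that is associated with each stratification variable". D6l gives a bias reason: "so that the estimated effect of the treatment is not biased due to differences in distribution of sex/gender or type of pain".

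**Analysis.** D6x, Hypothesis 1, analyses the pre- to post-treatment change in average pain by "analysis of covariance (ANCOVA) with treatment condition (HYP, MM, ED) as the explanatory variable and the baseline pain as a covariate". The secondary outcomes repeat this model with their own baseline value. The GEE for longer-term effects has group, time, their interaction and the pre-treatment value. None of these models contains sex/gender or pain type.

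**Where the factors do appear.** D6t introduces "covariates (variables to control for in planned analyses if needed", but the covariates in Table 4 are medical services utilization and medication use. Sex/gender and pain type are listed in Table 4 only as moderators, and D6x treats those analyses as exploratory.

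**Campus.** D6m says that in each four-month period "there will be two class options for each condition, one based in Seattle and one at American Lake". Campus is neither a stratification factor nor a model term.

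**The concern.** The design and the analysis do not match. Blocking within strata makes the arms alike on sex/gender and pain type, which removes part of the chance variation in the difference between arms. A model without those factors still counts their variance as noise. It therefore estimates the standard error as if allocation had ignored the strata.

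Precision that the trial has already bought is then missing from the confidence intervals and p-values. The error is on the safe side, because it does not create false positives. It matters because the power margin is thin in the weakest scenario in D6z, and because the missing terms are baseline data that the trial collects anyway.

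**Working it through.** **1. The plan's own figure.** Inputs from D6z: decreases of 0.3 (ED), 0.8 (HYP) and 0.6 (MM) as the weakest scenario, SD 1, 80 per arm, alpha 0.05.
- Mean of the three = 1.7/3 = 0.567. Squared deviations: 0.0711 + 0.0544 + 0.0011 = 0.1267.
- Noncentrality = 80 × 0.1267 / 1² = 10.13, with 2 and 237 degrees of freedom.
- Power = 81.6%, and 78 per arm would give 80%. The statement of at least 80% power with 80 per arm reproduces.

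**2. Size of the mismatch.** Let R² be the share of the planned model's residual variance that sex/gender and pain type explain. The documents give no value, so R² is assumed. With the strata balanced, the planned model's standard error is too large by the factor 1/√(1 − R²), and its F statistic is too small by the factor (1 − R²).

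The 5% critical value of F with 2 and 236 degrees of freedom (240 less 4 fitted terms) is 3.034. The true type I error is then about P(F > 3.034/(1 − R²)). For 2 numerator degrees of freedom this equals (1 + 2x/236)^(−118), where x = 3.034/(1 − R²). Power with the strata modelled uses noncentrality 10.13/(1 − R²).

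| Assumed R² | SE too large by | x | Type I error, planned model | Power, strata modelled |
|---|---|---|---|---|
| 0% | 0% | 3.034 | 5.0% | 81.6% |
| 2% | 1.0% | 3.096 | 4.7% | 82.4% |
| 5% | 2.6% | 3.194 | 4.3% | 83.6% |
| 10% | 5.4% | 3.371 | 3.6% | 85.7% |

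**3. Check by simulation.** Assumptions, none of them in the documents: 240 participants, permuted blocks of 6 in six strata (two sex/gender by three pain-type categories), and campus unstratified at 50:50. Strata explain 10% and campus 5% of variance. There were 5,000 replicates for the standard errors and 4,000 for the tests.
- True SD of a pairwise contrast from the planned model: 0.149 under stratified randomisation, against 0.160 under simple randomisation. The estimate keeps the gain.
- Standard error that the planned model reports: 0.158. With the strata in the model it is 0.150, and the true SD is 0.148. The ratio 0.1582/0.1501 = 1.054 agrees with the 5.4% above.
- Type I error of the planned model: 3.6%. With the strata modelled it is about 5%.
- Power in the weakest scenario: 81.6% planned, 85.1% with strata.

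With 5% for strata and 5% for campus, type I error is 4.3% and power goes from 81.9% to 83.3%. With 15% and 10%, type I error is 3.1% and power goes from 82.4% to 88.0%.

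**4. What a campus term would add.** Under the same three settings, campus on top of the strata takes power to 85.7% (5%, 5%), 87.3% (10%, 5%) and 92.1% (15%, 10%). This is ordinary covariate adjustment. Campus was not stratified, so the unadjusted standard error already allows for its chance imbalance.

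**The case against.** The best defence is that nothing is invalid. Both stated reasons for stratifying are met by the randomisation itself: the arms are balanced on the two factors, and the estimate is not distorted by them. The planned test errs on the conservative side, the stated power reproduces, and the loss may be as small as 1% of a standard error. All of this stands, and it limits the point to efficiency and to agreement between design and analysis. It does not answer the point, because the covariates held in reserve and the exploratory moderators do not put the strata into the primary model.

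Three stronger readings are tempting, and the documents do not support them.

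- *The variance reduction is lost.* It is not. The true spread of the estimate shrinks as intended (0.149 against 0.160 in the setting above). Only the reported standard error, interval and p-value fail to show it.
- *Campus fixes the group leaders and the patient source, so leaving it out biases the comparison.* No text says this. D6m states "Trained instructors will commit to offering three groups per year: one of each treatment type", so leaders are planned to be crossed with treatment. Section 1a says "Participants will be recruited from clinics at the Seattle and American Lake Campuses of VAPSHCS" and also names community clinics, without tying source to class location. Every condition runs at both campuses, so imbalance arises by chance only and averages zero over randomisations.
- *Later cohorts should be stratified by campus.* This appears moot. D5 ties the last enrolment increase to filling the final cohort, D6c says groups stop after cohort 12, and the current version is dated June 2020.

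A fair caution also applies to a campus term. The documents do not say when a research participant's campus is set. Preferred location is recorded for non-research participants only, and the schedule letter is described after assignment. If campus is chosen once the arm is known, it is a post-randomisation variable and adjusting for it would be unsound.

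**Conclusion.** The point holds as a matter of efficiency and of matching the analysis to the randomisation. Two stratification factors are missing from the primary ANCOVA, the secondary ANCOVAs and the GEE. The primary test is mildly conservative: for strata explaining 2% to 10% of residual variance, the standard error is about 1% to 5.4% too large and the true type I error about 4.7% to 3.6% instead of 5%. Modelling the strata would bring weakest-scenario power to between 82.4% and 85.7%. These sizes rest on the assumed R². If the strata explain nothing, there is no loss.

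A reader might infer that the sample size fails. It does not, since D6z makes no use of these terms and its figure reproduces without them. Campus is a possible further precision gain and not a source of systematic bias. Correlation among participants in the same class is a separate matter that neither strata nor campus terms would deal with.

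**What to change.** In D6x, before unblinding, define the primary model as change in average pain on treatment, baseline pain, sex/gender and pain type, with the categories used in the randomisation. Carry sex/gender and pain type into the secondary ANCOVAs and the GEE. Keep the current treatment-plus-baseline model as a sensitivity analysis.

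State the pain-type categories explicitly, because the list in D6l can be read as three or four. With two sex/gender categories the cost is 1 + 2 = 3 or 1 + 3 = 4 degrees of freedom out of about 240, plus one sentence of text and no new data.

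Add campus as a fixed effect only if the records show that it was set and recorded before allocation, and describe it as a precision term. If that cannot be shown, leave it out.
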